10.3 Statistical Analysis of Subjective Effects

Paired t-tests will be used to compare subjective effects measures at the Week 2 and 6 time points with the baseline (Week -1) values. This analysis will be conducted on the evaluable subjects in the PP population. If data are unexpectedly found not to be

normally distributed, an appropriate non-parametric test will be performed. Differences will be considered statistically significant at an alpha level of 0.05. The same SAS codes used in [Section 7.3](#) for paired t-test will be used for the analysis.

In addition, a linear mixed model analysis of variance will be used to compare the between product group differences in the absolute change from baseline values of each of the urinary and blood BoEs. The same statistical model and SAS codes used in [Section 7.3](#) for product group comparisons will be used for the analysis.

11. SAFETY

All case report form (CRF) data will be listed by subject and chronologically by assessment time points. This will include rechecks, unscheduled assessments, and early termination.

Applicable continuous variables will be summarized using n, arithmetic mean, SD, minimum, median, and maximum.

The level of precision will be presented as follows: minimum/maximum in the same precision as in the database, mean/median in one more precision level than minimum/maximum, SD in one more precision level than mean/median, and n will be presented as an integer.

Where individual data points are missing because of dropouts or other reasons, the data will be summarized based on reduced denominators.

11.1 Subject Discontinuation

Subjects will be summarized by number of subjects enrolled, completed, and discontinued the study with discontinuation reasons by product group and overall.

11.2 Demographics

Descriptive statistics will be calculated for continuous variables (age, weight, height, and body mass index) by product group and overall. Age will be derived from date of birth to date of informed consent.

Frequency counts will be provided for categorical variables (race, ethnicity, and gender) by product group and overall.

11.3 Tobacco Product Use History

Descriptive statistics will be calculated for number of cigarettes smoked per day and number of years used tobacco product based on the self-reported tobacco product use history by product group and overall.

Frequency counts will be provided for categorical variables (Cigarette brand, brand style, flavor, and size) by product group and overall.

11.4 Adverse Events

All adverse events (AEs) occurring during this clinical trial will be coded using the Medical Dictionary for Regulatory Activities (MedDRA[®]) Version 21.0.

All AEs captured in the database will be listed in by-subject data listings including verbatim term, coded term, product, severity, relationship to study medication, and action; however, only product-use-emergent AEs (PUEAEs) will be summarized.

A PUEAE is defined as an AE that is starting or worsening at the time of or after study product administration. Each PUEAE will be attributed to a product based on the onset date and time of the AE. If an AE increases in severity, that AE will be given a resolution date and time and a new record will be initiated with the new severity. If the severity of an AE remains the same or decreases, the AE will be kept open through to resolution.

If the onset time of an AE is missing and the onset date is the same as the product administration date, then the AE will be considered product use emergent in the prior product. If onset time of an AE is missing and the onset date does not fall on an administration date, then the AE will be considered product use emergent for the last product administered. If the onset date of an AE is missing, then the AE will be considered product use emergent and attributed to the product on the study.

PUEAEs will be tabulated by System Organ Class (SOC) and Preferred Term. Summary tables will include number of subjects reporting the AE and as percent of number of subjects used study product. The number of AEs will be tabulated in a similar manner. Tables which tabulate the number of TEAEs by severity and relationship to study product will also be included.

Serious adverse events (SAEs), if present, will also be listed. Applicable narratives will be included in the CSR.

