On Day 1 of Week 1, subjects will be randomly selected to either remain smoking their non-menthol (20 subjects) or menthol (20 subjects) UB cigarettes, or to switch to smoking non-menthol (50 subjects) or menthol (50 subjects) VLN cigarettes as per their UB cigarette flavor. Subjects will return at the end of Weeks 2 and 6, at the time indicated by the CRU, for collection of blood and 24-hour urine samples for BoE assessments. Subjective effects questionnaires will also be completed at scheduled times. Subjects will continue recording their CPD in their e-diaries. A subset of 18 non-menthol and 18 menthol smoker subjects will complete an assessment of puffing topography with the VLN

cigarettes at these visits, and a further subset of 12 non-menthol and 12 menthol smoker subjects will also complete an assessment of nicotine PK at the end of these visits. Subjects undergoing topography and PK assessments will have been assigned to switch to smoking VLN cigarettes.

Additionally, all subjects will visit the clinic at the end of Week 4 to receive further supplies of cigarettes (if assigned to the VLN groups) and to complete subjective effects questionnaires.

Subjects randomized to the VLN groups will be provided with a supply of VLN cigarettes at each visit, which will be 150 % of their usual daily consumption as reported during Week -1. If a subject runs out of cigarettes between clinic visits, they may visit the clinic to receive additional test cigarettes. All subjects will be asked to smoke their cigarettes *ad libitum*, recording their actual daily consumption in their e-diaries. Non-compliant nicotine product consumption should also be recorded. Used cigarette butts will also be collected during ambulatory periods to verify product use and/or assess compliance. During Week -1 (all subjects) and all subsequent weeks (subjects randomized to continue smoking UB cigarettes) subjects will be asked not to change their UB cigarette brand or flavor.

The CRU will attempt to contact all subjects who participated in the study (including subjects who terminate the study early) using their standard procedures approximately 7 days after the last contact to determine if any AE has occurred since the last study visit.

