5.12.6 Blood sampling for nicotine PK assessments

At clinic visits at the end of Weeks -1, 2 and 6, a randomly-selected subset of 12 non-menthol and 12 menthol smoker subjects will complete a nicotine pharmacokinetic assessment session with either their UB (Week -1) or the VLN (Weeks 2 and 6) cigarettes. These subjects will be/have been assigned to switch to smoking VLN cigarettes and will be selected from the subjects who undergo topography assessment. These assessments will only be performed at a single clinical site (Lincoln) and will take place on the morning following the 24-h confinement period.

Following the completion of the 24-hour urine collection period, selected subjects will remain in the clinic for a further night, in which they will abstain from smoking any cigarettes/using any nicotine-containing products for at least 12 hours prior to the PK assessment session. During this session, subjects will smoke a single cigarette *ad libitum* during a 5-minute period. A 4 ml blood sample for plasma nicotine analysis will be drawn into a plastic K2-EDTA (lavender top) vacutainer tube at -5, 2, 5, 7, 10, 12, 15, 30, 45, 60, 90, 120, 150 and 180 minutes relative to the start of cigarette smoking, as delineated in the [Summary of Study Events Tables](#). In total, approximately 144 ml of blood will be drawn from each of the selected subjects during the entire study for nicotine pharmacokinetic analysis.

The blood samples collected for plasma nicotine analysis may be kept at room temperature prior to centrifugation, and will be centrifuged at approximately 1000-1300 RCF at \sim 5°C for approximately 10 minutes, within 60 minutes from collection. After centrifugation, the plasma will be transferred to two methanol prewashed 3.5 ml polypropylene screw cap tubes. Samples will then be stored at approximately -20°C within 120 minutes of collection and until analyzed by Celerion Bioanalytical Services (Lincoln, Nebraska).

Samples will be analyzed using a validated liquid chromatography coupled to tandem mass spectrometry detection analytical method with the appropriate quality controls in

accordance with FDA Good Laboratory Practice (GLP) regulations (Title 21 Code of Federal Regulations [CFR] Part 58).

Additional instructions for collection, processing, and shipping of samples for nicotine PK assessments will be provided separately.

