5.12.11.1 Monitoring

The subjects will be instructed to inform the study physician or staff of any AEs and intercurrent illnesses experienced during the study. Additionally, a specific inquiry regarding AEs will be conducted during clinic visits, at End-of-Study (or upon early discontinuation), or during the follow-up telephone call. The inquiry will be posed in a non-specific manner using open-ended questions so as not to bias the response (e.g., How are you feeling today?).

A subject who has any clinically significant AE or clinically significant abnormal laboratory test value will be evaluated by the Investigator or other monitoring physician and will be treated and/or followed up until the symptoms or values return to normal or acceptable levels (as appropriate in the opinion of the Investigator), or until the subject is lost to follow-up. Where appropriate, medical tests and examinations will be performed to document resolution of the event(s).

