Table 12-1 Adverse Event Frequency - Number of Subjects Reporting the Event (% of Subjects Used Product)

[figure not shown]
Adverse Events*	Baseline	VLN Non-Menthолated	VLN Menthолated	UB Non-Menthолated	UB Menthолated	Overall#
Number of Subjects Used Study Product	XX (100%)	XX (100%)	XX (100%)	XX (100%)	XX (100%)	XX (100%)
Number of Subjects With Adverse Events	X (XX%)	X (XX%)	X (XX%)	X (XX%)	X (XX%)	X (XX%)
	X (XX%)	X (XX%)	X (XX%)	X (XX%)	X (XX%)	X (XX%)
General disorders and administration site conditions	X (XX%)	X (XX%)	X (XX%)	X (XX%)	X (XX%)	X (XX%)
Vessel puncture site pain	X (XX%)	X (XX%)	X (XX%)	X (XX%)	X (XX%)	X (XX%)
Vessel puncture site reaction	X (XX%)	X (XX%)	X (XX%)	X (XX%)	X (XX%)	X (XX%)

*Adverse events are classified according to MedDRA® Version 21.0
Subjects used their own usual brand cigarettes at Week -1.
Although a subject may have had 2 or more clinical adverse experiences, the subject is counted only once within a category. The same subject may appear in different categories.
Overall includes AEs after the start of Week1 product use.

Source: Table 14.3.1.1
Program: /CAXXXXX/sas_prg/stsas/intexttest/t_ae.sas DDMMYY HH:MM

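### Adverse events from PK sessions that only VLN subjects attend enter the VLN columns with no UB counterpart, and no table marks them

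*SAP*

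**What the plan says.** Protocol 2.1 randomises subjects "to switch to smoking non-menthol (50 subjects) or menthol (50 subjects) VLN cigarettes", with 20 per flavour staying on usual brand. Under Protocol 5.12.6, "a randomly-selected subset of 12 non-menthol and 12 menthol smoker subjects will complete a nicotine pharmacokinetic assessment session" at the end of Weeks -1, 2 and 6. All of them are in the VLN arm: "These subjects will be/have been assigned to switch to smoking VLN cigarettes and will be selected from the subjects who undergo topography assessment". After the 24-hour urine collection, "selected subjects will remain in the clinic for a further night", go without nicotine for at least 12 hours, smoke one cigarette and are sampled up to 180 minutes.

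On adverse events, Protocol 5.12.11.1 says that "a specific inquiry regarding AEs will be conducted during clinic visits". SAP 11.4 sets the attribution rule, "Each PUEAE will be attributed to a product based on the onset date and time of the AE", and the footnote to listing 16.2.7.1 assigns an event to the last product used before onset. Protocol 6.4 summarises emergent events whatever their relationship to product. Tables 12-1, 14.3.1.1 and 14.3.1.2 put the two VLN columns beside the two UB columns for the whole Safety population. An example row in the Table 12-1 shell is "Vessel puncture site pain". Table 14.3.1.3 adds severity and relationship to study product. No PK-subset split, procedure flag or footnote is planned.

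**The concern.** After the switch, the two arms do not have the same opportunity to generate or report an AE. About a quarter of each VLN column goes through a procedure, an abstinence period and extra supervised time that no UB subject has. Puncture-site reactions, dizziness or abstinence symptoms from those sessions would count as VLN product-use-emergent events. AEs are the only safety endpoint that Protocol 2.2 lists, and these tables will be read across their columns. The sponsor could see a VLN excess that comes partly from PK sampling, or could have trouble interpreting a real one.

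**Working it through.** **1. The plan's own figure.** Protocol 5.12.6 gives about 144 ml of PK blood per subject over three sessions at 4 ml per sample.
- 14 samples (Protocol 5.12.6): 3 × 14 × 4 = 168 ml.
- 15 samples (Protocol synopsis, SAP 9.1): 3 × 15 × 4 = 180 ml.
- 144 ml matches only 12 samples (3 × 12 × 4), which no schedule contains.

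The same method reproduces the BoE total in Protocol 5.12.4: 3 × (2 × 4 + 4) = 36 ml. The two PK schedules and the volume need to be reconciled. Both counts are carried below.

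**2. Imbalance.** PK subjects are 12/50 = 24% of each VLN column and 0/20 of each UB column. Samples after the switch number 24 × 2 × 14 = 672 or 24 × 2 × 15 = 720 in VLN, and 0 in UB. The Week -1 session precedes the switch, so its events belong in the Baseline column. Only Weeks 2 and 6 matter here.

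**3. Route into the tables.** In a Week 2 or 6 session the last product used is VLN, so an event then is a VLN event whatever its cause. Investigators rate causality only against product administration, on five levels (Protocol 5.12.11.2), with no study-procedure category. In the Table 14.3.1.3 shell, relationship by product group appears only in the total rows, not for each AE term.

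**4. Possible size.** Let b be the background AE incidence, equal in both arms, and q the risk of a procedure AE per session, independent over two sessions. The added share of VLN subjects with an AE is 0.24 × (1 − b) × [1 − (1 − q)²]. It cannot exceed 0.24, or 24 points. The documents give neither b nor q. With b = 20% assumed:

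| q (assumed) | Calculation | Added points |
|---|---|---|
| 5% | 0.24 × 0.8 × 0.0975 | 1.9 |
| 10% | 0.24 × 0.8 × 0.19 | 3.6 |
| 20% | 0.24 × 0.8 × 0.36 | 6.9 |

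The cap and these figures apply to counts of subjects (Tables 12-1 and 14.3.1.1). Table 14.3.1.2 counts events, so one subject can add several.

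**5. Venous accesses.** Protocol 5.12.6 does not say how the PK samples are drawn. If one access served each session (assumed), the VLN-only accesses number 24 × 2 = 48. The other post-switch accesses in VLN number 100 × 3 = 300 (BoE at Weeks 2 and 6, plus end-of-study laboratory tests), or 200 if the end-of-study sample shares the Week 6 draw. The VLN-only share is then 48/348 = 14% or 48/248 = 19%.

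**The case against.** The case for leaving the plan alone has real weight.

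- **Causality is recorded.** Emergent AEs are defined by timing, and Table 14.3.1.3 lets an event be classed as unrelated. This helps, but the study is open-label, causality is rated to product only, and the relationship split by group is not given by term. The main frequency tables ignore relationship.
- **Events can be partly separated.** Puncture-site terms identify themselves, and listings 16.2.7.1 and 16.2.5.3.1 give onset and sample times. A reader might infer that a real product effect could not be told apart from the procedure; the documents do not support that. What remains is that dizziness or abstinence-type events are ambiguous, and that nothing planned does the matching.
- **No between-group AE test is planned**, and safety is in neither the primary nor the secondary objectives. The bias is therefore confined to descriptive displays. Nor are the AE tables the only safety display by group, since vital signs are also summarised that way (SAP 11.6).
- **The shell rows are weak evidence.** SAP section 14 says that shells may not reflect every aspect of the study, the Table 14.3.1.1 shell has different example rows, and UB subjects also have venipuncture at Weeks 2 and 6. The point does not depend on those rows.
- **Chance may be larger.** At 20% incidence the standard error of a 100-versus-40 difference is √(0.16/100 + 0.16/40) = 7.5 points, about twice the 3.6-point illustration. That limits the practical weight, but the bias runs in a known direction and is cheap to deal with.

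**Conclusion.** The point holds as a limitation of the descriptive AE tables. PK-session events load the VLN columns only, and nothing planned marks them. The imbalance of 24% against 0% follows from the documents. The cap of 24 points on subject incidence follows from it. The effect on AE rates does not: the 3.6 points (1.9 to 6.9) rest wholly on assumed risks.

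A reader might divide samples and infer that 69% to 71% of post-switch blood draws in VLN have no UB counterpart (672/972 or 720/1,020). That treats each sample as a puncture, which the documents do not establish; with one access per session the share is 14% to 19%. Nor do the documents show that a VLN excess, if seen, would be an artefact. They show only that the planned frequency tables could not distinguish the two explanations.

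**What to change.** In SAP 11.4 and the AE table shells:

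1. Flag AEs in PK subjects at Weeks 2 and 6 with onset between the end of the 24-hour urine collection and a prespecified time after the last PK sample. Use the recorded times (listings 16.2.5.3.1 and 16.2.5.3.2), because no listing shell shows a discharge time. Also flag puncture-site terms in PK subjects after a session.
2. Add two supportive VLN-versus-UB AE tables: one excluding flagged events, and one restricted to subjects outside the PK subset (planned 100 − 24 = 76 VLN and 40 UB). Read any VLN-versus-UB statement on AEs alongside both.
3. Keep the full Safety-population tables unchanged.

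The cost is one flag and two tables from data already collected, with no new procedure. State the limits in the SAP. The restricted table has fewer VLN subjects. Its VLN site mix changes, because PK is done at one site only. It also retains 36 − 24 = 12 topography-only VLN subjects, whose sessions likewise have no UB counterpart. Excluding flagged events may remove some genuine VLN events, since a VLN cigarette is smoked in the session; that is why both tables are supportive only.

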Study Population	Seventy (70) self-affirmed, exclusive smokers each of non-mentholated and mentholated King-size cigarettes will be enrolled into the study.

Duration of Study Conduct	Screening events will occur within 28 days prior to Day 1 of Week -1. Subjects will participate in the study for a period of 7 weeks after the start of Week -1, with a follow-up call approximately 7 days after the last study visit.
Study Products and Summarization	
The study products are:
 
• Subject's UB non-mentholated filtered king size cigarettes• Subject's UB mentholated filtered king size cigarettes• Non-mentholated VLN cigarettes• Mentholated VLN cigarettes 
VLN cigarettes contain 0.4mg nicotine per gram of tobacco.
 
Subjects will smoke their assigned products ad libitum throughout the study. Product use will be listed by subject and summarized by time point (study week).

Consumption and Biomarker Data Parameters and Summarization	
During ambulatory periods between clinic visits, subjects will record daily cigarette use (CPD) in their e-diary, including both compliant and non-compliant (nicotine containing products other than their assigned product) use. Subjects will also collect used cigarette butts during these periods.
 
Twenty-four (24)-hour urine collections will be performed during clinic visits at the end of Weeks -1, 2 and 6, for BoE (total NNAL, total NNN, 3-HPMA, S-PMA, 1-OHP and T_{neq}) analysis. Creatinine will also be measured in each 24-hour collection and may be used to adjust the concentration values of the BoE if necessary. Blood samples for carboxyhemoglobin (COHb) and cotinine measurement will also be taken during these visits.
 
All data will be listed by subject and summarized by time point using descriptive statistics.

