⁸ Standard physical examination including oral cavity and oropharynx. A symptom driven examination can be performed at other time, at Investigator or designee's discretion.

⁹ Symptom driven and if deemed necessary.

¹⁰ Symptom driven and if deemed necessary based on the follow-up call. Subjects will visit the clinic for this to take place.

¹¹ Body weight only at Start of Week -1

¹² Body weight only at end of study

STUDY EVENTS/ASSESSMENTS	Screening ¹	Clinic Visits					Out-of-CRU Between Clinic Visits		
		Start of Week -1	End of Week -1 (baseline)	End of Week 2	End of Week 4	End of Week 6			
Clinical Chemistry ¹³ , Hematology, Urinalysis	X							X	
Urine Drug and Alcohol Screen	X	X	X	X	X	X		X	
HIV, HBsAg, and HCV Serology	X								
Serum Pregnancy Test (females)	X								
Serum FSH Test ¹⁴	X								
Urine Cotinine Screen	X	X							
Exhaled CO Measurement	X	X							
Test Product (VLN cigarette) Trial	X								
Provide Smoking Cessation Information ¹⁵	X							X	X
Review of AEs	X ¹⁶	X	X	X	X	X		X	X
Urine Pregnancy Test (females)		X	X						
Review Restrictions on Smoking and Nicotine Product Use	X	X	X	X	X	X			
Reminder Contacts to return to the CRU ¹⁷		X ¹⁸					X ¹⁹		
Test Product Dispensing			X	X	X				

¹³ Clinical chemistry tests will be performed after at least an 8 hour fast; however, in case of dropouts or rechecks, subjects may not have fasted for 8 hours prior to the clinical chemistry sample being taken.

¹⁴ Postmenopausal females only

¹⁵ Subjects will be referred to the Quit Assist® website

¹⁶ AE recording to begin immediately after the product trial at Screening.

¹⁷ Phone calls or texts or instant messages (as per site preference) reminding subjects of clinic visits.

¹⁸ The day prior to clinic visit at start of Week -1 subjects will be contacted.

¹⁹The day prior to clinic visits at end of Weeks -1, 2, 4 and 6 subjects will be contacted.

STUDY EVENTS/ASSESSMENTS	Screening ¹	Clinic Visits					Out-of-CRU Between Clinic Visits		
		Start of Week -1	End of Week -1 (baseline)	End of Week 2	End of Week 4	End of Week 6			
Dispense Canisters for Used Cigarette Butt Collection		X	X	X	X				
Used Cigarette Butt Collection							X		
Used Cigarette Butt Canister Return			X	X	X	X			
24-hour Urine Collection for BoE analysis			X	X		X			
Plasma Sample for Cotinine Analysis			X	X		X			
Blood Sample for COHb Analysis			X	X		X			
Puffing Topography ²⁰			X	X		X			
Blood Samples for Nicotine PK Analysis ²¹			X	X		X			
Training on e-diary use		X							

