5.7 Follow-Up Call

The CRU will attempt to contact all subjects who participated in the study (including subjects who terminate the study early) using their standard procedures approximately 7 days after the last contact. This will be to:

- Review AEs and concomitant medication use

- Provide smoking cessation information

A symptom-driven physical examination may also be required, in which case subjects will return to the clinic for this to take place.

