6.4 Safety

All clinical safety data will be listed by subject and time point as appropriate. The following items will be summarized using n, arithmetic mean, SD, median, minimum, and maximum for continuous data and frequency counts for categorical data.

- Subject disposition
- Subject demographics
- Tobacco product use history

- Vital signs

All events captured in the database will be listed in by-subject data listings. However, only study product use-emergent AEs will be summarized. A study product use-emergent AE is defined as an AE that is starting or worsening at the time of or after the first study product use (i.e., Product Trial).

Frequencies of subjects with study product use-emergent AEs, regardless of relationship to study product will be summarized and sorted by system organ class. Frequencies of subjects with study product use-emergent serious AEs will be likewise summarized. Frequencies of study product use-emergent AEs will be summarized by severity and relationship to study product.

Changes in physical examinations (if any) will be described in the text of the final report. All concomitant medications recorded during the study will be listed by subject.

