Musculoskeletal pain	X (X%)	X (X%)	X (X%)	X (X%)	X (X%)	X (X%)
Nervous system disorders	X (X%)	X (X%)	X (X%)	X (X%)	X (X%)	X (X%)
Headache NOS	X (X%)	X (X%)	X (X%)	X (X%)	X (X%)	X (X%)

Note: *Adverse events are classified according to MedDRA Version 20.0. ^ = Product-use-emergent adverse events
 Subject used their usual brand at Baseline (Week -1).

VLN non-mentholated = Non-mentholated VLN cigarettes

VLN mentholated = Mentholated VLN cigarettes

UB non-mentholated = Subjects' UB non-mentholated filtered cigarettes

UB mentholated = Subjects' UB mentholated filtered cigarettes

Overall includes AEs after the start of Week1 product use.

Program: /CAXXXXX/ECR/sas_prg/stsas/tab prgrname.sas DDMMYYYY HH:MM

Post-text Table 14.3.1.2 will be in the following format:

Page 1 of X

Table 14.3.1.2 Product-Use-Emergent Adverse Event Frequency -
 Number of Adverse Events (% of Total Adverse Events) (Safety Population)

Adverse Event*	Baseline	VLN Non- Mentholated	VLN Mentholated	UB non- Mentholated	UB Mentholated	Overall#
Number of PUEAEs	XX (XXX%)	XX (XXX%)	XX (XXX%)	XX (XXX%)	XX (XXX%)	XX (XXX%)
Eye disorders	X (X%)	X (X%)	X (X%)	X (X%)	X (X%)	X (X%)
Vision blurred	X (X%)	X (X%)	X (X%)	X (X%)	X (X%)	X (X%)
Gastrointestinal disorders	X (X%)	X (X%)	X (X%)	X (X%)	X (X%)	X (X%)
Dyspepsia	X (X%)	X (X%)	X (X%)	X (X%)	X (X%)	X (X%)
Nausea	X (X%)	X (X%)	X (X%)	X (X%)	X (X%)	X (X%)
Musculoskeletal and connective tissue disorders	X (X%)	X (X%)	X (X%)	X (X%)	X (X%)	X (X%)
Back pain	X (X%)	X (X%)	X (X%)	X (X%)	X (X%)	X (X%)
Muscle cramps	X (X%)	X (X%)	X (X%)	X (X%)	X (X%)	X (X%)
Musculoskeletal pain	X (X%)	X (X%)	X (X%)	X (X%)	X (X%)	X (X%)
Nervous system disorders	X (X%)	X (X%)	X (X%)	X (X%)	X (X%)	X (X%)
Headache NOS	X (X%)	X (X%)	X (X%)	X (X%)	X (X%)	X (X%)

Note: *Adverse events are classified according to MedDRA Version 20.0. ^ = Product-use-emergent adverse events
 Subject used their usual brand at Baseline (Week -1).

VLN non-mentholated = Non-mentholated VLN cigarettes

VLN mentholated = Mentholated VLN cigarettes

UB non-mentholated = Subjects' UB non-mentholated filtered cigarettes

UB mentholated = Subjects' UB mentholated filtered cigarettes

Overall includes AEs after the start of Week1 product use.

Program: /CAXXXX/ECR/sas_prg/stsas/tab prgrname.sas DDMMYY HH:MM

Post-text Table 14.3.1.3 will be in the following format:

Page 1 of X

Table 14.3.1.3 Product-Use-Emergent Adverse Event Frequency by Severity and Relationship to Study Product -

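### AE percentages in the Baseline column cannot be compared with those in the VLN or UB columns: observation time differs, and the Baseline window is not defined

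*SAP*

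**What the plan says.** SAP 11.4 sets the statistic for the subject-level AE tables: "Summary tables will include number of subjects reporting the AE and as percent of number of subjects used study product". No subject-time or exposure-adjusted rate appears in SAP 11.4, in the list of outputs in SAP 13, or in the AE shells.

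The shells for Tables 12-1 and 14.3.1.1 have six columns: Baseline, VLN non-mentholated, VLN mentholated, UB non-mentholated, UB mentholated and Overall. The footnote to Table 14.3.1.1 describes the first column: "Subject used their usual brand at Baseline (Week -1"). A second footnote separates it from the rest: "Overall includes AEs after the start of Week1 product use". Table 14.3.1.2 has the same columns but gives events as a percent of total AEs. Table 14.3.1.3 gives counts, with Baseline as a row.

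The start of AE collection is earlier than the footnote suggests. The protocol's Summary of Study Events has "AE recording to begin immediately after the product trial at Screening". Protocol 6.4 counts an AE as product-use-emergent if it is "starting or worsening at the time of or after the first study product use (i.e., Product Trial"). SAP 11.4 attributes each emergent AE to a product by its onset but does not mention the product trial. It does not say in which column an AE between the trial and the start of Week -1 belongs.

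**The concern.** The percent of subjects with at least one event rises with the length of observation. A column headed Baseline, placed beside the product columns of a before-and-after study, invites the reader to set one against the other. If the windows differ in length, an unchanged AE rate will look like an increase after Week 1, in smokers who switched and in smokers who did not. At stake is the reading of a descriptive safety table. The primary and secondary endpoint analyses are not affected.

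The undefined window makes this worse. If trial-to-Week -1 events go into Baseline, the column has a different length for each subject and mixes events after a few VLN cigarettes with events on usual brand. If they go elsewhere or are dropped, the column is one week long. The reader cannot tell which applies.

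**Working it through.** The documents state no AE rate or ratio, so there is no figure of the plan's to reproduce.

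**Window lengths**
- On-study time (protocol synopsis, Duration of Study Conduct): "Subjects will participate in the study for a period of 7 weeks after the start of Week -1". Week -1 takes 1 week, leaving 7 − 1 = 6 weeks on assigned product.
- Follow-up (protocol 5.7): the site calls "using their standard procedures approximately 7 days after the last contact" and reviews AEs, which extends the product columns to about 6 + 1 = 7 weeks.
- Baseline as footnoted: 1 week.
- Longest possible Baseline: "Screening events will occur within 28 days prior to Day 1 of Week -1". From the product trial to the end of Week -1 this is up to 28 + 7 = 35 days, or 5 weeks.

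**Model (assumed)**
The hazard λ of a first AE is constant and the same for every product. Then p(t) = 1 − exp(−λt). With an assumed six-week incidence p(6), λ = −ln(1 − p(6))/6. The apparent excess is p(6)/p(b) or p(7)/p(b) for a Baseline of b weeks.

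Example at p(6) = 30%: λ = −ln(0.70)/6 = 0.0594 per week, so p(1) = 5.8% and p(7) = 34.0%. The excess is 30/5.77 = 5.2 at six weeks and 34.0/5.77 = 5.9 at seven.

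**One-week Baseline, no product effect**

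| Assumed p(6) | p(1) | Excess at 6 weeks | Excess at 7 weeks |
|---|---|---|---|
| 2% | 0.34% | 5.95 | 6.93 |
| 10% | 1.74% | 5.74 | 6.64 |
| 30% | 5.77% | 5.20 | 5.90 |
| 50% | 10.91% | 4.58 | 5.08 |
| 70% | 18.18% | 3.85 | 4.15 |
| 90% | 31.87% | 2.82 | 2.92 |

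The range is 2.8 to 6.9, or about 3- to 7-fold.

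**Longer Baseline, p(6) = 30%**

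| Baseline (weeks) | p(b) | Excess at 6 weeks | Excess at 7 weeks |
|---|---|---|---|
| 2 | 11.21% | 2.68 | 3.04 |
| 3 | 16.33% | 1.84 | 2.08 |
| 5 | 25.71% | 1.17 | 1.32 |

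**VLN against UB**
Both sets of columns start at Week 1 and end at the same planned point. Under an equal hazard both show 30% at six weeks, a ratio of 1.0 with no adjustment. In expected numbers that is 15 of 50 in each VLN group, 6 of 20 in each UB group, and 140 × 0.0577 = 8.1 of 140 at a one-week Baseline.

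**With rates instead of percentages**
Take an event rate of 0.0594 per week, with everyone completing and six weeks counted:
- Baseline: 140 × 1 = 140 subject-weeks, 8.3 events.
- Each VLN group: 50 × 6 = 300 subject-weeks, 17.8 events.
- Each UB group: 20 × 6 = 120 subject-weeks, 7.1 events.

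Each is 5.9 per 100 subject-weeks, so the artefact disappears.

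**The case against.** The strongest reply is that nothing in the plan rests on this comparison. Paired tests against Week -1 are specified for consumption, topography, biomarkers, PK and subjective effects, and none for AEs. Safety is not among the study objectives, although AEs are a listed endpoint. Baseline is kept out of Overall. The concurrent UB columns in the same table would rise over Baseline just as the VLN columns do, which warns a careful reader that the rise is not due to VLN. All of this stands, and it keeps the point to a presentational improvement.

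A second reply is that the one-week length rests on a footnote, while AE recording begins up to 28 days before Week -1. That is correct. It lowers the possible excess, but it does not make the column readable, because the window is then unknown and varies between subjects.

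A reader might infer more than the documents support:
- *That the tables make VLN in particular look worse.* They do not. The UB columns cover the same planned window and carry the same excess.
- *That every AE table is in percent of subjects.* Table 14.3.1.2 uses percent of total AEs and Table 14.3.1.3 uses counts. Event numbers in both still grow with time.
- *That early withdrawal biases VLN against UB.* It could, if withdrawal differs between groups. Protocol 6.1.1 expects less non-compliance in the UB groups, and protocol 3.5 lists non-compliance as a reason for discontinuation. But no withdrawal rates are given, and disposition is tabulated by group.

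**Conclusion.** The point holds for Tables 12-1 and 14.3.1.1. Their Baseline percentages are not comparable with any product column, VLN or UB. With a one-week Baseline the product columns would show about a 3- to 7-fold excess with no product effect. With a five-week Baseline the excess is about 1.2- to 1.3-fold at 30% six-week incidence. These sizes rest on a constant hazard equal across products and on assumed incidences from 2% to 90%; none of these comes from the documents. A several-fold excess is therefore one reading of the shells, not a certainty.

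VLN against concurrent UB is fair on planned exposure and is the AE comparison the SAP should name. The change is worth making because it is cheap and removes an ambiguity, not because a planned conclusion depends on it.

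**What to change.** In SAP 11.4 and the AE shells:

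1. Define the Baseline AE window by its start and end, and state which column holds AEs from the Screening product trial to the start of Week -1.
2. Put subject-weeks of observation in each column header, over the same window as the events counted, and say whether the follow-up week is included.
3. Show events per 100 subject-weeks beside the percentages.
4. State that VLN versus concurrent UB is the AE comparison, and that any Baseline-versus-product statement uses the rates only.

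The dates needed are already in the planned listings: product trial (Appendix 16.2.5.2.1), randomization and completion or discontinuation (16.2.1.1), AE onset (16.2.7.1) and follow-up call (16.2.8.4). The work is SAP and shell wording plus a small programming change, and the tables become slightly wider. A separate column for events after Week 6 is optional and not needed for this point.
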